4.1.4 Clinical experience and safety of disulfiram

Disulfiram was first advocated as a therapy for alcoholism in 1937 when it was noted that rubber factory workers exposed to the molecule became intolerant of alcohol. Disulfiram has been approved by the FDA since 1951 for the treatment of alcohol dependence. Given its unusual history and early drug development, the quality of evidence supporting its use is limited. Nonetheless, a recent multicenter observational study in Italy found that disulfiram statistically significantly reduced COVID-19-related symptoms (fever and dyspnea) in a cohort of 752 individuals taking disulfiram (dosing range 100-800 mg daily) for the treatment of alcohol dependence compared to 542 COVID-19+ controls.⁹¹ There were a total of only 4 cases and 4 controls who were admitted to be able to determine whether disulfiram prevented hospitalizations due to COVID-19. Reviews of disulfiram outcome studies spanning several decades have found that only one of more than 40 clinical trials have met current adequate research design criteria and only five of 135 disulfiram clinical trials have had a controlled design.⁹²

The mechanism for the drug's alcohol deterrent effects lie in its ability to inhibit liver mitochondrial aldehyde dehydrogenases (ALDH).⁹³ This enzyme converts acetaldehyde to acetate in alcohol metabolism leading to an immediate uncomfortable reaction upon exposure to alcohol and when inhibited leads to the buildup of acetaldehyde.⁹⁴ The reaction to alcohol usually consists of symptoms such as flushing, heat sensation, nausea, vomiting, palpitations, headaches, and/or circulatory changes such as decreased blood pressure or increased pulse rate. The time to onset of ALDH inhibition which is sufficient to result in a reaction upon alcohol consumption is 12 hours and ALDH function is completely restored within 6 days of stopping disulfiram in alcoholics.^{33,95}

The current recommended dose of disulfiram is 250 to 500 mg once daily. When disulfiram was first used clinically almost sixty years ago, it was common practice to use doses up to 1 to 3 grams.⁹⁶ However, these higher doses were associated with reports of severe adverse reactions, particularly in those individuals who continued to be exposed to alcohol.⁹⁷ Many of the serious adverse effects of disulfiram, such as psychotic reactions, hypotension and neuropathy, are thought to be dose-related,⁹⁶ and most fatal reactions occurred in patients who were taking more than 500 mg a day of disulfiram and who consumed more than 28 grams of alcohol.^{98,99}

Given the variability in the clinical and biologic effect of disulfiram (see below), early recommendations by manufacturers and experts were to confirm that the drug was indeed active by challenging patients with alcohol. One recommended approach was to administer four 200 mg tablets (800 mg total) of disulfiram on the first day, reducing by one tablet each subsequent day until the fifth day, when patients were administered a single pill (200 mg) and then challenged with a dose containing 15-30 mL of pure ethanol.¹⁰⁰ In one study of 63 patients using this approach, 33 required 200 to 300 mg, 17 required 400 to 500 mg, 6 required 600 to 700 mg and 7 required 800 to 1500 mg in order to develop a clinical reaction to ethanol. During longer-term dosing, significant side effects were uncommon, but included drowsiness and mild confused states; these side effects waned in one to three days after dose reduction

or cessation.¹⁰⁰ Other approaches to deal with the patient-to-patient variability in activity were to administer very high doses. In one study, doses up to 6 grams per day were given.¹⁰¹ Disulfiram was reported to be safe, although with chronic dosing rare but significant liver complications occurred that may or may not have been drug-related.¹⁰²

4.1.5 HIV clinical trials of disulfiram

Our group has performed clinical trials of disulfiram in the setting of HIV cure trials, which have demonstrated safety and tolerability at doses as high as 2000 mg.^{103,104} In a phase 2b dose escalation trial in HIV-infected virally suppressed participants, we evaluated disulfiram given at 500 mg, 1000 mg or 2000 mg daily for 3 consecutive days (NCT01944371).²⁹ Disulfiram was well tolerated at all doses studied; there were no drug discontinuations or grade 2-4 adverse events observed. These safety data were consistent with our prior phase 1 trial evaluating disulfiram 500 mg daily administered for 14 consecutive days in HIV-infected virally suppressed participants (NCT01286259).¹⁰⁴ A follow-up study in HIV-infected participants was performed, this time in combination with a histone deacetylase inhibitor, vorinostat (SAHA) (NCT03198559). In this phase 2b trial, HIV-infected virally suppressed participants received 2000 mg of oral disulfiram once daily for 28 days but this time, in combination with 400 mg oral vorinostat once daily on days 8-10 and again on days 22-24 (for a total of 6 days total of vorinostat overlap). Although there was evidence that this combination did reverse HIV latency, the study was halted due to two participants experiencing neurological adverse events including confusion, lethargy ataxia and paranoia. All symptoms resolved after discontinuation of both study drugs, disulfiram and vorinostat. Review of the participants' clinical records was unable to completely rule out that disulfiram administration, in combination with vorinostat, was related to these adverse events. Therefore, for the proposed work, we will only be administering disulfiram alone, as was demonstrated to be safely given in our prior phase 2b dose escalation trial.²⁹

4.1.6 Pharmacology of disulfiram

Overview. The metabolism of disulfiram is complex (Figure 5).¹⁰⁵⁻¹⁰⁷ Disulfiram is metabolized to diethyldithiocarbamate (DDTC) and then to diethyldithiocarbamate methyl ester (DDTC-Me). DDTC-Me is formed by thiol S-methyl ester transferase from DDTC. DDTC-Me is then metabolized to S-methyl-N-N- diethylthiocarbamate (disulfiram carbamate, or DETC-Me), and then bioactivated to S-methyl-N-N- diethylthiolcarbamate sulfoxide (DETC-MeSO). DETC-MeSO inhibits ALDH and hence is responsible for the anti-alcohol effect.^{106,108} With regard to the anti-alcohol activity, most investigators—including [name], who lead the PK study outlined below—focused on latter metabolites (DETC-Me and DETC-MeSO).

Bioactivation of disulfiram to the active metabolite DETC-MeSO occurs principally via CYP 3A4/5, with contributions by CYP 1A2, 2A6 and 2D6.^{107,109} Faiman and colleagues reported that the reduced

[figure not shown]

Figure 5. Disulfiram metabolism. Disulfiram is rapidly metabolized to its metabolites, including DDTc, DDTc-Me, DETC-Me, DETC-MeSO, and carbamathione.

A formal study of the elimination kinetics of disulfiram was performed by Faiman and colleagues and reported in 1984.¹¹¹ Fifteen alcoholics (all men) were given 250 mg as a single dose on day 1 and day 12. The observed half-life of disulfiram, diethyldithiocarbamate (DDTC), diethyldithiocarbamate-methyl ester (DDTC-Me), diethylamine (DEA), and carbon disulfide were found to be 7.3, 15.5, 22.1, 13.9, and 8.9 hours, respectively. Disulfiram is reported to be 90% eliminated in 3 days.¹¹² Peak plasma levels for disulfiram and its metabolites occurred at approximately 8 to 10 hours after the dose, while peak levels of carbon disulfide occurred 5 to 6 hours after the dose. There was marked variability in plasma levels of disulfiram and its metabolites (see Figure) which was attributed in part to plasma protein binding (disulfiram is 95% protein bound) and/or differences in liver metabolism.¹¹³ It has also been suggested that

metabolite of disulfiram, diethyldithiocarbamate (DDTC), inhibits several CYP enzymes including CYP 3A4/4, 2E1, and 2A6 which all play a role in bioactivation of disulfiram to DETC-MeSO.¹⁰⁹ This effect has been postulated as a reason why disulfiram produces variable reactions when alcohol is co-consumed.¹⁰⁹

The pharmacokinetics and pharmacodynamics of disulfiram are highly variable between individuals. Up to 50% will not have a disulfiram-ethanol reaction on the recommended 250 mg dose.¹⁰⁰ For some, doses up to 500 mg are insufficient to cause a disulfiram-ethanol reaction.¹⁰⁰ This creates a clinical challenge in finding a dose of disulfiram that will be effective to elicit a mild disulfiram-ethanol reaction, while maintaining the safety of the patient should he or she drink alcohol while on the medication.¹¹⁰

[figure not shown]

Figure 6. Seven-compartment pharmacokinetic model of disulfiram (DSF) metabolism. CL, clearance (L/hour); DSFGUT, amount of disulfiram in gut (mg); DSFPLASMA, amount of disulfiram in plasma (mg); ka, absorption constant; knon-lin, nonlinear elimination calculated using Km and maximum rate of metabolism (Vmax) terms; M1PLASMA, amount of N,N-diethyldithiocarbamate (DDTC) in plasma (mg); M2PLASMA, amount of diethyldithiocarbamate-methyl ester (DDTC-Me) in plasma (mg); M3PLASMA, amount of S-methyl-N, N-diethylthiolcarbamate sulfoxide (DETC-MeSO) in plasma (mg); M3PERIPHERY, amount of DETC-MeSO in plasma (mg); M4PLASMA, amount of carbamathione in plasma (mg); Q, blood flow (L/hour); V, volume of distribution (L).

disulfiram undergoes enterohepatic recycling. In a separate earlier study reported in 1979, a 600-fold variation in disulfiram plasma concentrations was reported.¹¹⁴ Other studies have noted high variability in levels of key metabolites.

More recently, our group performed a detailed pharmacokinetic/pharmacodynamic (PK/PD) modeling study based on our phase 2b dose escalation HIV cure clinical trial.^{29,34} Parent drug (disulfiram) and four metabolites (DDTC, DDTC-Me, DETC-MeSO and carbamathione) were quantified and measured over the 31-day study period, as well as viral outcome measures for the PD analysis (cell-associated HIV RNA in CD4+ T cells and plasma HIV RNA). A comprehensive seven-compartment PK/PD model was built to estimate disulfiram metabolism (Figure 6). Higher doses of

administered disulfiram were associated with higher plasma concentrations of parent drug and metabolites (Figure 7). A linear PK model simultaneously incorporating all metabolites underpredicted plasma concentrations in the 2000 mg group, which initially appeared to be due to supraproportional concentrations of disulfiram in the highest dosing group (Table 1). However, after fitting a PK model allowing for nonlinear elimination kinetics, the supraproportional concentrations seemed to be largely explained by reduced elimination (e.g., due to saturation of CYP enzymes at higher concentrations) rather than increased bioavailability at the 2000 mg dose.

4.1.7 Table 1. Final PK model estimates for median AUC_{0-72} exposure to metabolites by dosing cohort.

	DSF (Disulfiram)	M1 (DDTC)	M2 (DDTC-Me)	M3 (DETC-MeSO)	M4 (Carbamathione)
500 mg group	3,186 (3,140–3,281)	2,826 (2,651–3,602)	2,309 (1,563–3,397)	1,563 (1,324–2,544)	4,295 (4,041–4,923)
1000 mg group	8,386 (7,419–12,861)	7,511 (4,974–14,886)	4,154 (3,416–6,000)	3,225 (2,102–5,383)	8,640 (7,232–19,379)
2000 mg group	22,331 (18,482–35,102)	20,362 (15,114–31,421)	7,048 (6,248–9,701)	8,643 (6,279–9,976)	25,167 (16,058–32,086)

DSF, parent drug; disulfiram; M1, metabolite 1; M2, metabolite 2; M3, metabolite 3; M4, metabolite 4; DSF, disulfiram; DDTC, N,N-diethyldithiocarbamate; DDTC, diethyldithiocarbamate-methyl ester; DDTC-MeSO, S-methyl-N,N-diethylthiolcarbamate sulfoxide.

^aMedian AUC_{0-72} estimate with 2.5 to 97.5 percentile range.

Disulfiram concentrations were significantly associated with increases in HIV cell-associated RNA (with an Emax of 78% and AUC_{50} of 1600 mg·hr/L for the parent compound) for all of the dosing cohorts. Similarly, each of the four metabolites were also shown to significantly increase cell-associated RNA. Disulfiram concentrations were also associated with an increase in plasma HIV RNA levels, but only in the highest (2000 mg) dosing group.^{29,34}

[figure not shown]

Figure 7. Plasma disulfiram concentrations by dosing group. Elevated plasma drug concentrations were observed with higher administered dose of disulfiram, which was safe and well tolerated all doses studied. Supraproportional concentrations of disulfiram were observed in the 2000 mg dose, which was largely attributed to decreased elimination (rather than increased bioavailability) in the PK model.

4.1.8 Disulfiram dose justification

Disulfiram's safety profile has been evaluated in several clinical trials.

In an open-label clinical trial to determine short-term disulfiram on decay of the HIV reservoir in patients on highly active antiretroviral therapy (NCT01286259), patients received 500 mg disulfiram daily via oral administration for 14 days. The safety and tolerability of a two-week course of disulfiram was defined using the Division of AIDS Table for Grading the Severity of Adult and Pediatric Adverse Events, Version 1.0, December 2004 (Clarification, August 2009). A total of 16 patients were recruited, with no adverse event reported during the treatment course.

In a phase 2 non-randomized trial focusing on short-term disulfiram to reverse latent HIV infection (NCT01944371),¹⁰³ patients received disulfiram daily for 5 days at doses of 500 mg, 1000 mg or 2000 mg. The safety and tolerability of disulfiram was defined using the Division of AIDS Table for Grading the Severity of Adult and Pediatric Adverse Events version 2.0, November 2014. Thirty patients were recruited, and all participants completed the study. There were no deaths, drug discontinuations, or grade 2-4 adverse events observed. No adverse events related to the study drug were reported in the 500 mg group, which was consistent with the findings described in the previous trial above. Grade 1 clinical adverse events related to study drug were more common in the higher dosing cohorts including 10 events in the 1000 mg group, and 14 events in the 2000 mg group.

4.1.9 SARS-CoV-2 viral load quantification

Serial SARS-CoV-2 viral load quantification will be performed using quantitative reverse transcription polymerase chain reaction (rtPCR) using the Roche MagNA Pure 96 (MP96) System.⁴ A modified CDC protocol was used to target the N1 and N2 gene of SARS-CoV-2 RNA, and this assay has been validated across multiple patient tissue types.¹¹⁵ The assay will be used to evaluate SARS-CoV-2 viral decline in those receiving or not receiving disulfiram. These assays will be performed on nasopharyngeal (NP) swabs, but also from blood samples. In addition, saliva will be collected and stored for potential future quantification of SARS-CoV-2 RNA and anti-SARS-CoV-2 IgA.

4.1.10 Preliminary data demonstrating the ability to enroll acute COVID+ patients

At the onset of the global COVID-19 pandemic, we rapidly developed the acute COVID-19 Host Immune Response Pathogenesis (CHIRP) study to evaluate clinical, demographic, behavioral, immunologic, and genetic risk factors associated with COVID-19 acquisition and severity. In order to minimize the potential risk of SARS-CoV-2 transmission to non-research patients, as well as household members to potentially infected research staff, we developed a study design for example,

allowing outpatient in-person visits using a mobile research van in order to abide by the Centers for Diseases Control guidelines for discontinuation of home isolation (<https://www.cdc.gov/coronavirus/2019-ncov/hcp/disposition-in-home-patients.html>). In less than four weeks of cohort development, we obtained study protocol approval, set up the off-campus location and mobile study van, and implemented strict infection control protocols to enroll COVID+ individuals and close household contacts. In order to minimize exposure time during in-person visits, electronic informed consent and release of information are obtained by phone. Longitudinal biospecimen collection are performed at weeks 1, 2, 4, 8, and 24 from baseline visit, collecting blood, urine, stool, saliva, and home expectorated sputum. To date, a total of 13 (26%) of 50 prospective screened participants have been enrolled in the study after just three weeks from study initiation, including four individuals and four family clusters. Among the first 13 participants enrolled, 62% are female, with a median age of 42 years. We will now leverage this intensive sampling cohort infrastructure to rapidly enroll participants for the DISCO trial.

5.1 Study objectives

5.1.1 Primary objective

- To determine the effect of oral disulfiram given at 1000 mg daily (cohort 1) or 2000 mg daily (cohort 2) versus placebo for 5 consecutive days in adults with early mild-to-moderate symptomatic SARS-CoV-2 infection on inflammation (plasma cytokine levels - e.g., IL-6, IL-1 β) using the MesoScale Diagnostics high sensitivity plasma cytokine platform²

5.1.2 Secondary objectives

- To determine the effect of oral disulfiram (2000 mg daily given for 5 consecutive days) in adults with early mild-to-moderate symptomatic SARS-CoV-2 infection on:
 - The safety and tolerability of oral disulfiram 2000 mg/day given for 5 consecutive days in adults with symptomatic SARS-CoV-2 infection.
 - SARS-CoV-2 PCR positivity and quantitative viral load using qRT-PCR on the Roche MagNA Pure 96 system.⁴
 - COVID symptom severity (using an adapted SSS-8 five-point symptom scale for common COVID-19 symptoms³ which abide by the FDA Guidance: Assessing COVID-19-Related Symptoms in Outpatient Adult and Adolescent Subjects in Clinical Trials of Drugs and Biological Products for COVID-19 Prevention or Treatment.¹¹⁶
 - The proportion of participants hospitalized at day 5, 15, and 31.
 - The proportion of participant deaths at day 5, 15, and 31.

5.2 Study Definitions

- *Enrolled*: From time consented to participate until designated as (i) ineligible based on the inclusion/exclusion criteria or withdraws, (ii) been discontinued from the study or (iii) completed the study.
- *Randomized*: when a randomization number is assigned.
- *Screen Failures*: signed informed consent, but then determined to be ineligible or withdraws before being randomized.
- *Discontinued*: randomized, but then withdrawn by investigator or participant withdraws consent.
- *Completed*: Participants are considered completed when they are followed through to day 31, had an adverse event or death occurred prior to day 31.

5.3 Study Population

5.3.1 Inclusion Criteria

1. Willing and able to provide written informed consent, and
2. Age \geq 18 years, and
3. Recent symptomatic COVID-19 disease (<14 days from symptom onset)

4. Recent SARS-CoV-2 positive test by molecular diagnostic assay within the preceding 7 days, and
5. Not currently hospitalized, and
6. Willing to abstain from any alcohol during the two-week period in which disulfiram will be administered and during the two-week period immediately after disulfiram administration.
7. Both male and female participants are eligible. Females of childbearing potential must have a negative pregnancy test at screening and agree to use a double-barrier method of contraception throughout the study period.

5.3.2 Exclusion Criteria

1. Pregnant, breastfeeding, or unwilling to practice birth control during participation in the study
2. Active malignancy requiring systemic chemotherapy or surgery in the preceding 3 months or for whom such therapies are expected in the subsequent 6 months
3. Decompensated liver disease as defined by the presence of ascites, encephalopathy, esophageal or gastric varices, or persistent jaundice
4. Serious illness requiring systemic treatment and/or hospitalization in the 3 months prior to study enrollment
5. Concurrent treatment with immunomodulatory drugs, and/or exposure to any immunomodulatory drug in the 4 weeks prior to study enrollment (e.g. corticosteroid therapy equal to or exceeding a dose of 15 mg/day of prednisone for more than 10 days, IL-2, interferon-alpha, methotrexate, cancer chemotherapy). NOTE: use of inhaled or nasal steroid is not exclusionary.
6. Serious medical or psychiatric illness that, in the opinion of the site investigator, would interfere with the ability to adhere to study requirements or to give informed consent.
7. Current alcohol use disorder or hazardous alcohol use (>7 drinks per week for women or > 14 drinks per week for men) as determined by clinical evaluation.
8. Current use of any drug formulation that contains alcohol or that might contain alcohol
9. Current use of warfarin.
10. Current use of oral lopinavir/ritonavir solution (and the inability to switch to a solid dosage form during the entire duration of the study).
11. ALT or AST > 2 x the upper limit of normal or total bilirubin outside the normal range.
12. Creatinine clearance (CrCl) < 50 mL/min by Cockcroft-Gault)
13. Allergy to rubber or thiuram derivatives

Note: Receipt of medications with potential anti-COVID activity that are considered standard-of-care at the study site (e.g., small molecules or monoclonal antibodies directed against SARS-CoV-2) is permitted during the trial. Prior receipt of current standard of care inpatient COVID-19 treatment, including remdesivir, convalescent plasma/sera, and dexamethasone,¹¹⁷ is also permitted and should be recorded as a prior medication.

5.3.3 Participant Withdrawal

Participants can terminate study participation and/or withdraw consent at any time without prejudice. Randomized participants who withdraw from the study will not be replaced. If a participant discontinues study dosing (for example, as a result of an AE), every attempt should be made to keep the participant in the study and continue to perform the required study-related follow-up and procedures (see Section 8.1, Criteria for Discontinuation of Study Treatment). The investigator may withdraw participants if they are non-compliant with study procedures or if the investigator determines that continued participation in the study would be harmful to the participant or the integrity of the study data.

5.3.4 Treatment

A total of 60 participants will be randomized (2:1) to receive active drug versus placebo in a dose escalation study. The first 30 participants will be enrolled in the 1000 mg dosing cohort, randomized 2:1 to receive either disulfiram 1000 mg (N=20) or placebo (N=10) daily for 5 consecutive days. As long as safety monitoring criteria are met to proceed to the second dose, the next 30 participants will be enrolled in the 2000 mg dosing cohort, randomized 2:1 to receive either disulfiram 2000 mg (N=20) or placebo (N=10) daily for 5 consecutive days.

5.3.5 Randomization

Participants enrolled in the study will be randomized using a web-based randomization procedure to receive active drug or no therapy at a 2:1 ratio within each dosing cohort.

5.3.6 Study drug administration

Drug will be administered within 72 hours of randomization.

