5.5 Study procedures by day

5.5.1 Screen and Baseline (Day -3 to Day 1)

1. Informed consent (obtained before performing study related activities)
2. Questionnaire Evaluation to include the COVID-19 Index Initial General questionnaire, COVID-19 Index Initial Substance Use, Reproductive Health survey, and Mental Health Supplemental Form
 - Demographics: Age, sex, race
 - Medical history: acute and chronic medical conditions that are risk factors for COVID – e.g., diabetes, cardiovascular disease, chronic obstructive pulmonary disease.
 - Transmission history: timing of exposure to COVID-19 source patient
 - Medications, allergies
 - Any medical condition arising after consent to be recorded as AE
 - Prior COVID-19 testing history (SARS-CoV-2 RT-PCR or antibody): positive test PCR required within 7 days of screening must be documented
 - COVID-19 symptom screen: 5-point ordinal adapted somatic symptom scale (SSS-8)³
3. Targeted physical exam and vital signs (temperature, heart rate, blood pressure, respiratory rate, oxygen saturation by pulse oximetry)
4. Clinical lab collection (run in real-time)
 - a. Screening labs: **complete** blood count with differential, urea, electrolytes, creatinine, calcium, magnesium, phosphate, liver function tests
 - b. Clinical labs associated with severe COVID: erythrocyte sedimentation rate (ESR), high sensitivity C-reactive protein (hs-CRP), D-dimer, lactate dehydrogenase (LDH), and ferritin.
 - c. Clinical labs to confirm COVID+ status: SARS-CoV-2 NP swab PCR assay
 - d. Females of childbearing potential: plasma beta-hCG urine pregnancy test
 - e. HIV+ participants: a CD4+/CD8+ T cell count and standard plasma HIV RNA assay.
5. Samples collected for research (run in batch at end of study enrollment)
 - a. Saliva for host DNA sequencing and potential future SARS-CoV-2 quantification (RNA levels and anti-SARS-CoV-2 IgA)
6. Randomization of those found to be eligible

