5.5.2 Study Drug/ Placebo Administration (Day 1)

5.5.2.1 Pre-Dose (Between Hour -0.5 and 0)

1. Questionnaire Evaluation to include the Index Follow up Questionnaire
2. Targeted physical exam and vital signs
3. Clinical lab collection

4. Samples collected for research (storage)
 - a. Blood: PBMC (CyTOF, single cell sequencing), plasma (plasma SARS-CoV-2 viral load), serum (SARS-CoV-2 serology)
 - b. Nasopharyngeal swab for SARS-CoV-2 viral load
 - c. Saliva for host DNA sequencing and potential future SARS-CoV-2 quantification (RNA levels and anti-SARS-CoV-2 IgA)

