6.2 Statistical Analysis

All main analyses will be conducted on an intention-to-treat basis. Models will assess the relationship between the timing of disulfiram treatment initiation relative to symptom onset and study outcomes for key efficacy/activity endpoints. The model will be fitted using generalized estimating equations (GEE) to handle the repeated measurements, where the comparison between randomized arms will use a two-sided Wald test. Levels of plasma inflammatory biomarker levels will be compared between arms using non-parametric Wilcoxon rank-sum tests (e.g., separately on days 5 and 15) considering results below the assay limit as the lowest rank. For the analysis of the SARS-CoV-2 viral loads, for the comparison of the proportion of participants with detectable SARS-CoV-2 RNA, we will use binary regression, with adjustment for risk stratum and pre-treatment SARS-CoV-2 RNA level.

For longitudinal analyses, we will perform both statistical summaries at each time point and comprehensive regression modeling. For the regression model, a full non-linear mixed effects (NMLE) model will be developed for disulfiram including all 60 participants across the 5 dosing days. The pharmacokinetics of disulfiram and the measured metabolites will be described by compartmental models parameterized in terms of clearance from the central compartment, apparent central and peripheral Vd and intercompartmental clearance. This will be followed by a full covariate screening process and then inclusion into the pharmacokinetic model. This may include covariates like drug interactions due to other therapy, weight, sex and other biologically plausible covariates collected during the study. From the final model, we will provide the AUC₀₋₇₂, C_{min}, and C_{max} for each patient.

For the primary pharmacodynamics response (plasma inflammatory biomarker levels – e.g., IL-6) the PK and PD data will be combined and analyzed simultaneously by nonlinear mixed-effects modelling (NONMEM version 7.1, Globomax LLC, Hanover, PA). Data will be analyzed using the first-order conditional estimation method with interaction, and ADVAN6 will be used to solve the differential

equations. Both empiric and mechanistic based pharmacodynamics models will be evaluated to describe the concentration effect relationship with the primary pharmacodynamics response.

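### Randomizing at Screen/Baseline, up to 72 hours before the first cytokine sample and dose, risks avoidable losses from the intention-to-treat set that moving the assignment to Day 1 would prevent

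*Combined protocol and SAP*

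**What the plan says.** - **Timing of assignment.** Section 5.5.1 covers Day -3 to Day 1, and its sixth and last step is "Randomization of those found to be eligible". Section 5.2 counts a participant as randomized once a number has been assigned; no dose is needed.
- **Gap to treatment.** Section 5.3.6: "Drug will be administered within 72 hours of randomization".
- **First research blood.** Section 5.5.2.1 takes plasma, serum and PBMC on Day 1, between half an hour before the dose and the dose itself. The schedule of evaluations shows none of these at Screen/Baseline, where the only research sample listed is saliva.
- **Replacement.** Section 5.3.3: "Randomized participants who withdraw from the study will not be replaced". The same section asks that people who stop dosing be kept in follow-up.
- **Analysis.** Section 6.2: "All main analyses will be conducted on an intention-to-treat basis". No modified set requiring a dose, a baseline or a later value is defined. Section 6.1 adjusts the IL-6 comparison for the pre-treatment level.
- **Missing baseline.** Section 6.2 allows a screening value to stand in where one exists.

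**The concern.** In an acute outpatient illness, some people may change their mind or drop out of contact within three days. Under the current order, anyone who does so after the web assignment but before Day 1 has used up a randomization number and contributes nothing to the primary endpoint. Someone who misses the Day 1 draw but returns later lacks the covariate that the primary comparison adjusts for. The screening-value fallback cannot supply it, because no cytokine sample is scheduled at screening.

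A cohort has only 10 placebo participants, so each one lost is a tenth of that cohort's control arm. The stated power carries no allowance for loss. The analyst would have to decide after the fact how to treat people who were randomized but have no cytokine data.

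**Working it through.** **Inputs from the documents.** 20 disulfiram and 10 placebo per cohort (section 5.3.4). From section 6.1: mean IL-6 36.7 pg/mL, a 35% difference, SD 12 (printed as ng/mL, read here as pg/mL), alpha 0.05. Section 6.2 gives a two-sided test.

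**Assumed.** A loss rate between randomization and the Day 1 draw of 2-10%. The documents state none.

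**1. The plan's own power.**
- Difference: 0.35 x 36.7 = 12.845.
- Standard error for 20 v 10: 12 x sqrt(1/20 + 1/10) = 4.648.
- Power: Phi(12.845/4.648 - 1.960) = Phi(0.804) = 0.789, which matches the stated figure of about 80%.

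The match is for one cohort on the raw scale, with every randomized participant evaluable.

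**2. Expected losses.** 60 x 0.02 = 1.2 to 60 x 0.10 = 6 participants in the trial.

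**3. Chance of losing at least one of 10 placebo participants in a cohort**, 1 - (1 - q)^10:

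| q | Chance |
|---|---|
| 2% | 1 - 0.98^10 = 18% |
| 5% | 1 - 0.95^10 = 40% |
| 10% | 1 - 0.90^10 = 65% |

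**4. Effect on precision and power**, with information = 1/(1/n1 + 1/n2) and power as in step 1:

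| Evaluable | Information | Change | Power |
|---|---|---|---|
| 20 v 10 | 6.67 | none | 0.789 |
| 20 v 9 (one placebo lost) | 6.21 | -7% | 0.760 |
| 18 v 9 (10% lost in both arms) | 6.00 | -10% | 0.746 |

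With a t-based calculation the three powers are 0.761, 0.729 and 0.712, so the drop is of similar size.

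**5. Sensitivity to the reading of section 6.1.** That section assumes log-normal IL-6. On the log scale (SD 0.319, from 12/36.7), power for 20 v 10 is 0.937 for a ratio of 0.65 and 0.681 for a ratio of 1.35. Pooling both cohorts on the raw scale (40 v 20) gives 0.974. The power levels therefore depend on the reading; the information losses in step 4 for a single cohort do not.

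**The case against.** A reader might infer that everyone whose course changes in the gap has no baseline, no dose and no outcome, and that the primary analysis cannot include them. The documents do not support that.

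- Seventy-two hours is a ceiling. The visit window also allows randomization and dosing on the same day, and the blood-volume list labels the screening visit Day 0.
- Section 5.3.3 asks for continued follow-up after dosing stops, and section 5.3.8 keeps participants hospitalized during the study in it. A person admitted before the first dose can still give Day 5, 15 and 31 samples. Only withdrawal of consent or loss to follow-up leaves no cytokine data.
- Screen/Baseline does collect hs-CRP, ferritin, D-dimer, LDH, blood count and the symptom scale. What it lacks is the cytokine value.
- The Wilcoxon comparisons of biomarker levels in section 6.2 are described without baseline adjustment. The same section offers median substitution and multiple imputation for missing covariates. Someone with a Day 5 value and no baseline can therefore be analyzed.

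All of this stands, and it narrows the affected group. A second tempting inference is bias. The trial is double-blind and nothing in the documents points to loss that differs by arm, so that is not shown either.

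It can also be said that one sentence defining the intention-to-treat set would cover dropout at any time. That sentence is worth having, but it would not recover the lost participants. Finally, the documents give no reason for the early assignment, but they do not describe how blinded drug is prepared, so a practical reason cannot be excluded.

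**Conclusion.** The point holds as a cheap improvement. The order of events allows a participant to be randomized before any cytokine sample exists, and the plan neither replaces that participant nor says how one with no cytokine data is handled.

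The size is modest: about 3 points of power for one placebo loss in a cohort and about 4 points for 10% loss in both arms. These figures assume that the lost participants have no usable cytokine data, that the comparison is within one cohort on the raw scale, and that the SD is in pg/mL. The 2-10% loss rate is an assumption, not a finding.

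The documents also do not tie cytokine measurement to a named visit sample. Section 5.5.2.1 labels the Day 1 plasma for viral load, and section 6.2.5 lists day 0 titers although the schedule shows no plasma or serum before Day 1. The conclusion takes the schedule as governing.

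**What to change.** Move the randomization step out of section 5.5.1 and into the Day 1 visit, in this order: confirm eligibility, complete the pre-dose questionnaire and samples, obtain the web assignment, dispense the first dose. Amend section 5.3.6 to match. People lost before that point become screen failures under section 5.2. The cohort can then fill to 20 and 10 with a pre-treatment sample planned for everyone randomized.

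In the same amendment, reconcile the day 0 titers in section 6.2.5 with the schedule, and the synopsis screening window (up to 7 days before randomization) with the Day -3 start in section 5.5.1. State in section 6.2 how randomized participants without a pre-treatment or later cytokine value are handled.

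**Cost.** Protocol wording, plus blinded kits for both arms at the Day 1 visit. Some extra screening is likely: at the assumed loss rates, 30/0.98 = 30.6 to 30/0.90 = 33.3, so 31 to 34 eligible people per cohort to randomize 30. No dose or clinical rule changes.
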